7.2 Assessments

Following informed consent, patients will be required in clinic at the times described in the Assessment Schedule (see Section 5.3 for screening and 7.2.2 for treatment)

Please note that for cohort (B)ii only the Day 0 assessment is arranged as below:

- Physical examination and central and local samples should be taken pre-ibrutinib treatment. The first dose should be on either a Monday or Tuesday to allow for sample delivery
- Central samples should be taken four hours post-ibrutinib administration

For all cohorts, on Day 1, (24 hrs post 1st dose), the blood sample should be taken before the patient begins the obinutuzumab infusion.

Every effort should be made to adhere to the protocol scheduled visits. Visits from months 1 onwards should be scheduled as close as possible but may be scheduled within +/- 7 days. HMDS assessments at other points:

- Following detection of MRD negativity, assessment times will change. Please see Section 7.2.3)
- If there is a clinical need for an additional bone marrow examination—e.g. to identify cause of cytopenia—please send the sample to HMDS for analysis (see section 7.3)

7.2.1 Details of assessments during treatment

Physical examinations:

- Blood pressure
- Pulse
- Temperature
- Weight
- ECOG performance status

A physical examination of the disease should also be included in each clinical assessment, this involves:

- Lymph node disease: the size of the largest lymph nodes in each nodal area (cervical, axillary and inguinal) should be measured in centimetres in 2-dimensions.
- Liver and spleen: If palpable, size of liver and spleen below costal margin should be measured

Constitutional symptom assessment:

- Assessment of B symptoms: fatigue, unintentional weight loss, fevers and night sweats.

Local Laboratory tests:

Haematology

IcICLE

Protocol

- Haemoglobin
- Lymphocyte count
- Neutrophil count
- Platelet count
- Reticulocyte count
- White blood cell count (with differential count)

Biochemistry

- Albumin
- Alkaline Phosphatase (ALP)
- ALT or AST
- Calcium (adjusted)
- Creatinine
- eGFR
- LDH
- Phosphate
- Potassium
- Sodium
- Total Bilirubin
- Total Protein
- Urea
- Urate

Immunology:

- Direct coombs test
- Serum immunoglobulins and electrophoresis
- β_2 microglobulin concentration

CT scans:

- CT scan of the thorax, abdomen and pelvis should be performed to assess lymph node disease

CT scans will be performed locally at IcICLE trial sites and reports may be requested for central review by members of the TMG. Redacted reports (where the patient is identified only by TNO) will be requested by email.

ECG

- 12 lead ECG should be performed to assess patients for signs of atrial fibrillation at Month 1 of treatment.

7.2.2 Assessment schedule

Day 0 pre-ibrutinib treatment (cohort (B)ii only)

- Samples for central analysis
 - Peripheral blood sample 4 x 5 mL in EDTA
- Local laboratory tests
- Complete physical examination

Day 0 4 hrs post 1st ibrutinib treatment (cohort (B)ii only)

- Samples for central analysis
 - Peripheral blood 2 x 5mL in EDTA
- Local laboratory tests
- Local immunology

Day 1 (before the 1st obinutuzumab treatment)

- Samples for central analysis:
 - Peripheral blood 2 x 5mL in EDTA
- Complete physical examination
- Local laboratory tests

Day 2

- Samples for central analysis:
 - Peripheral blood 2 x 5mL in EDTA
- Complete physical examination

- Local laboratory tests

Day 8 and Day 15

- Samples for central analysis:
 - Peripheral blood 2 x 5mL in EDTA
- Local laboratory tests

Month 1

- Samples for central analysis (bone marrow samples not required for IcICLLe patients who have transitioned to the Extension Study):
 - Peripheral blood 4 x 5mL in EDTA
 - Bone Marrow Aspirate (EDTA)
 - Bone Marrow Trepine Biopsy (directly in formalin)
- Complete physical examination
- Constitutional symptom assessment
- ECG
- Local laboratory tests
- Disease Response according to modified IWCLL criteria (Appendix 1 & 2)

Month 3

- Samples for central analysis:
 - Peripheral blood 2 x 5mL in EDTA
- Complete physical examination
- Local laboratory tests
- CT scan

Month 6

Cohort (A) and B(i) (IcICLLe):

- Samples for central analysis:
 - Peripheral blood 4 x 5mL in EDTA
 - Bone Marrow Aspirate (EDTA)
 - Bone Marrow Trepine Biopsy (directly in formalin)
- Disease Response according to modified IWCLL criteria (Appendix 1 & 2)

Cohort (B)ii & (B)iii (IcICLLe Extension Study):

- Samples for central analysis
 - Peripheral blood 2 x 5mL in EDTA

All Cohorts

- Complete physical examination
- Constitutional symptom assessment
- Local laboratory
- Local immunology
- CT scan: should only be performed if the result of the 3 month scan was abnormal.

Month 9

Cohort (A) and (B)i (IcICLLe):

- Samples for central analysis:
 - Peripheral blood 2 x 5mL in EDTA

Cohort (B)ii & (B)iii (IcICLLe Extension Study):

- Samples for central analysis:
 - Peripheral blood 4 x 5mL in EDTA
 - Bone Marrow Aspirate (EDTA)
 - Bone Marrow Trepine Biopsy (directly in formalin)
- Disease Response according to modified IWCLL criteria (Appendix 1 & 2)

All Cohorts

- Complete physical examination
- Local laboratory tests

Month 12 and every 6 months thereafter

- Samples for central analysis:
 - Peripheral blood 2 x 5mL in EDTA
- Complete physical examination
- Local laboratory tests

7.2.3 MRD negative remission (all patients)**Assessments to confirm MRD negative remission**

All patients will receive treatment on IcICLLe until MRD negativity has been confirmed or until disease progression, whichever is earliest. Confirmation of complete MRD negativity is given by the HMDS once MRD negativity has been recorded for 6 months.

As per IWCLL guidelines, (refer to Appendix 1 for these guidelines and references), MRD negativity should be measured by three consecutive MRD negative peripheral blood (PB) results at 3 month intervals. To confirm the remission 6 months after the first MRD negative PB sample, a bone marrow (BM) examination should be performed with the third blood sample, both PB and BM aspirate should be sent to the HMDS for analysis of the MRD level.

At 6 months following clinical complete remission or the first MRD negative peripheral blood result (as described above), the following assessments should be undertaken to confirm the remission.

- Samples for central analysis:
 - Peripheral blood 4 x 5mL in EDTA
 - Bone Marrow Aspirate (EDTA)
 - Bone Marrow Trepine Biopsy (directly in formalin)
- Complete physical examination
- Constitutional symptom assessment
- CT-scan should be performed to confirm clinical complete MRD negative remission.
- Local blood biochemistry and haematology
- Local Immunology

If the bone marrow does not confirm MRD negativity, the patient should continue to receive ibrutinib/obinutuzumab until disease progression.

Should a patient be confirmed to be in MRD-negative remission by the bone marrow examination, trial treatment will cease according to the MRD negative remission stopping rules (7.2.3.1). At the end of the extended treatment period defined by the stopping rules, we would strongly recommend that a BM sample is sent with a PB sample to HMDS 2-4 weeks prior to the scheduled stopping date for ibrutinib to confirm the level of continued MRD response.

Subsequently, a patient in MRD-negative remission should be monitored by peripheral blood samples taken every 6 months and sent to HMDS for analysis. During this monitoring period an optional BM sample may be requested to confirm PB results.

7.2.3.1 MRD negative remission stopping rules

MRD will be measured in the peripheral blood and bone marrow at the time-points described in section 7.2.3 above. The MRD negative confirmation date is defined as the date of the first MRD negative peripheral blood (PB) sample. MRD negative status must be confirmed by subsequent PB and bone marrow (BM) assessment within 6 months of the first MRD negative sample.

Patients receiving treatment on IcICLLe who become MRD negative will stop therapy as described below. MRD monitoring will continue according to the trial visit schedule.

Patients receiving ibrutinib + obinutuzumab

- If PB is MRD negative **during** the 6 cycles of obinutuzumab treatment, and MRD negative remission is confirmed by PB and BM assessment, the participant will receive 12 months further ibrutinib from the end of obinutuzumab treatment. If the patient remains MRD negative after these 12 months of further treatment, ibrutinib will be stopped.
- If PB is MRD negative **after** the 6 cycles of obinutuzumab, and MRD negative remission is confirmed by PB and BM assessment, patients will receive further ibrutinib treatment to double the duration of ibrutinib treatment¹⁵ from the first MRD negative PB sample. If the patient is still MRD negative at the end of this extra treatment time, ibrutinib will be stopped.
For example:
 - If the patient has their first MRD negative blood sample at 9 months, the patient will receive 9 months further ibrutinib treatment: 18 months in total.

Patients receiving ibrutinib monotherapy

- If PB is MRD negative after 12-18 months of ibrutinib treatment, and MRD negative remission is confirmed by PB and BM assessment, patients will receive further ibrutinib to double the duration of treatment from start of ibrutinib to the first MRD negative sample. If the patient remains MRD negative in the PB after this period of treatment, ibrutinib will be stopped.
For example:
 - If the patient has their first MRD negative blood sample at 12 months, the patient will receive 12 months further ibrutinib treatment: 24 months in total.
 - If the patient is confirmed MRD negative with a BM at 15 months, the patient will receive 15 months further ibrutinib treatment: 30 months in total.
- If PB is MRD negative at or after 24 months ibrutinib treatment, and MRD negative remission is confirmed by PB and BM assessment, a further 18 months of ibrutinib will be given from the first MRD negative sample. If the patient is still MRD negative in the PB at the end of the 18 months further ibrutinib treatment, ibrutinib will be stopped.

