7.2.3.2 MRD analysis reports from HMDS

The following diagnostic categories will be used on HMDS reports to define MRD status:

- B-cell chronic lymphocytic leukaemia (B-cell CLL)
 - Applies to cases with high levels of residual disease: more than 5 x 10⁹/l circulating CLL cells or 30% CLL cells in the BM,
- B-cell CLL – MRD-positive at iwCLL threshold (≥0.01%)
 - Applies to cases with residual disease detectable at or above the iwCLL 0.01% threshold and so not to be considered for treatment cessation.
- B-cell CLL – MRD-negative at iwCLL threshold (<0.01%)
 - Applies to cases eligible for stopping rules, either with no detectable residual disease or with very low levels of detectable disease below 0.01%.
- Other diagnoses, e.g. “see comments” or “inadequate sample”
 - Applies to cases in which the MRD status cannot be determined at the 0.01% threshold. Interpretation of cases with such a diagnosis should be reviewed by the CI and the Clinical Coordinators.

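### Final ibrutinib stop check on monotherapy: Section 7.2.3.1 stops on negative blood, while Section 7.2.3.2 bars cessation for a marrow at or above 0.01%

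*Protocol*

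**What the plan says.** Section 7.2.3.1 works in two steps. The first is confirmation of the remission, which needs both compartments in every cohort: "MRD negative status must be confirmed by subsequent PB and bone marrow (BM) assessment within 6 months of the first MRD negative sample". Section 7.2.3 gives the consequence if that confirmatory marrow is positive: "If the bone marrow does not confirm MRD negativity, the patient should continue to receive ibrutinib/obinutuzumab until disease progression".

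The second step comes after a further period of ibrutinib and decides whether the drug is stopped. It is worded differently by regimen:

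- Monotherapy, first negative blood at 12-18 months: "If the patient remains MRD negative in the PB after this period of treatment, ibrutinib will be stopped".
- Monotherapy, first negative blood at or after 24 months: "If the patient is still MRD negative in the PB at the end of the 18 months further ibrutinib treatment, ibrutinib will be stopped".
- Combination, blood negative during the six obinutuzumab cycles: "If the patient remains MRD negative after these 12 months of further treatment, ibrutinib will be stopped".
- Combination, blood negative after the six cycles: "If the patient is still MRD negative at the end of this extra treatment time, ibrutinib will be stopped".

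Two other statements bear on the second step. Section 7.2.3 says that, at the end of the extended period, "we would strongly recommend that a BM sample is sent with a PB sample to HMDS 2-4 weeks prior to the scheduled stopping date". Section 7.2.3.2, which defines the central laboratory's report categories, says of the MRD-positive category: "Applies to cases with residual disease detectable at or above the iwCLL 0.01% threshold and so not to be considered for treatment cessation". These categories are not confined to blood, since the highest one is defined partly by a marrow percentage.

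**The concern.** A marrow sample requested just before the scheduled stop can disagree with the blood. The monotherapy rules look only at blood, and Section 7.2.3.2 attaches a bar on cessation to the report category, whichever compartment was sampled. No text says which instruction governs.

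What is at stake is whether a treatment-stopping instruction can be carried out consistently. Two monotherapy patients with the same blood and marrow results could be handled differently according to which subsection the site followed. Combination patients have no named compartment to go by.

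**Working it through.** No figure in the protocol is in dispute, so the check is a comparison of the texts. Take a patient whose remission was confirmed earlier in blood and marrow, who has completed the extended ibrutinib, and whose pre-stop samples show blood below 0.01% and marrow at or above 0.01%.

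| Branch in 7.2.3.1 | Compartment named for the final check | 7.2.3.1 | 7.2.3.2, from the marrow report | Result |
|---|---|---|---|---|
| Monotherapy, first negative at 12-18 months | Blood | Stop | Not for cessation | Contradiction |
| Monotherapy, first negative at 24 months or later | Blood | Stop | Not for cessation | Contradiction |
| Combination, negative during the cycles | None | Either reading | Not for cessation | Ambiguity |
| Combination, negative after the cycles | None | Either reading | Not for cessation | Ambiguity |

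So 2 of 4 branches contradict Section 7.2.3.2 and 2 of 4 are ambiguous. If the recommended marrow is not taken, there is no marrow report. The monotherapy patient is then stopped on blood and no conflict appears.

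The consequence stated in Section 7.2.3 for a non-confirming marrow does not settle the matter. It belongs to the confirmation step, about 6 months after the first negative blood sample. The pre-stop marrow is introduced later in the same section with no consequence attached.

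Timing of the stops against the outcomes, in months of ibrutinib treatment:

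- Monotherapy, first negative at Month 12: 12 + 12 = Month 24.
- Monotherapy, first negative at Month 24 or later: at least 24 + 18 = Month 42.
- Combination, negative during the cycles: end of obinutuzumab (about Month 5-6) + 12 = about Month 17-18.
- Combination, first negative at Month 9: 9 + 9 = Month 18. First negative at Month 12: 12 + 12 = Month 24.
- Primary outcome: assessed at or before Month 6 (initial phase) or Month 9 (extension), earlier than every stop above.

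The contradictory branches therefore produce no stop before Month 24, the 2-year point for progression-free survival. Stops before that point occur only in the combination branches, and there only when blood is first negative early enough.

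**The case against.** The strongest defence is that Section 7.2.3.2 only defines laboratory report labels. Its negative category is described in terms of eligibility for the stopping rules, which suggests screening at entry, and a positive marrow at entry already means that treatment continues. On that reading there is no conflict at the final check. The reading is possible, but the section does not limit itself to entry or to blood, and its wording concerns cessation, which happens at the second step. It could also be said that the pre-stop marrow is informational. The protocol does not say so.

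The rest of the defence stands and limits the point. A reader might infer that the whole stop decision rests on blood. It does not: marrow confirmation is required in all four branches before the extended period begins. A reader might also infer that combination patients receive opposite instructions. The documents do not support that, because those branches name no compartment and, read with the two-compartment definition of MRD-negative remission in Section 12.1.1, are compatible with not stopping. Finally, a site that does not take a recommended test and acts on blood is following the protocol as written, which is not itself a contradiction.

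**Conclusion.** The point holds for the final stop check on ibrutinib monotherapy: two written instructions oppose each other for a patient with negative blood and a positive pre-stop marrow. For ibrutinib plus obinutuzumab it holds only as an ambiguity.

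The number of patients affected cannot be derived. The documents give no rate of blood-marrow discordance at a second check in patients already confirmed negative in both compartments, and the conflict needs the recommended marrow to have been taken. Section 12.2.2 expects a negligible proportion of patients to become MRD negative on ibrutinib alone. That sentence gives no time horizon, so later negativity is not ruled out, but few patients should reach the contradictory branches.

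A reader might infer that 2-year progression-free survival depends on which subsection a site followed. The documents do not support this for the contradictory branches, whose stops fall at Month 24 or later. The earlier stops belong to the combination branches, where the wording is unclear but not opposed. The primary outcome is unaffected.

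This is a contradiction between stated rules on stopping treatment and more than a missing detail. It is worth correcting even though few patients are likely to meet it.

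**What to change.** Reconcile Sections 7.2.3, 7.2.3.1 and 7.2.3.2:

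- In each of the four branches of 7.2.3.1, name the compartment or compartments that decide the final stop.
- In 7.2.3, state what follows when the pre-stop marrow disagrees with the blood.
- In 7.2.3.2, align the cessation wording with that rule, and say whether it applies at confirmation, at the final check, or at both.

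Which rule applies is for the sponsor to decide. The cost is wording in three adjoining subsections. If the sponsor makes marrow decisive, the sample that is now recommended would be needed for every patient at a scheduled stop, and the protocol should say so. Otherwise no new procedure is required.

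### In the 12-18 month monotherapy stopping rule (Protocol 7.2.3.1), the second worked example doubles time to the confirming marrow, but the rule doubles time to the first negative blood, so they differ by up to 6 months of ibrutinib

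*Protocol*

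**What the plan says.** Protocol section 7.2.3.1 sets the date that counts for all patients: "The MRD negative confirmation date is defined as the date of the first MRD negative peripheral blood (PB) sample". Confirmation follows later: "MRD negative status must be confirmed by subsequent PB and bone marrow (BM) assessment within 6 months of the first MRD negative sample".

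For patients on ibrutinib alone there are two branches. The first opens with "If PB is MRD negative after 12-18 months of ibrutinib treatment" and, once blood and marrow have confirmed the remission, directs that "patients will receive further ibrutinib to double the duration of treatment from start of ibrutinib to the first MRD negative sample". Two examples follow:

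- The first reads "If the patient has their first MRD negative blood sample at 12 months, the patient will receive 12 months further ibrutinib treatment", which the protocol sums to a course of 24 months.
- The second reads "If the patient is confirmed MRD negative with a BM at 15 months, the patient will receive 15 months further ibrutinib treatment", which it sums to a course of 30 months.

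The second branch, for negativity at or after 24 months, also counts from the first negative sample: "a further 18 months of ibrutinib will be given from the first MRD negative sample". The worked example for the combination regimen does the same (first negative blood at 9 months, 9 further, 18 in total).

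Section 7.2.3 gives the confirmation schedule: "three consecutive MRD negative peripheral blood (PB) results at 3 month intervals", with the marrow taken alongside the third blood, 6 months after the first.

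**The concern.** The definition, the rule, the first monotherapy example, the combination example and the 24-month branch all count from the first negative sample. Only the second monotherapy example counts from a marrow. Doubling the time to a later date gives a longer course than the rule prescribes.

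Section 7.2.3 says treatment ceases according to these rules, so this is an operative dosing instruction, and sites are likely to consult the worked examples when setting a stop date. A site that copies the second example would keep a patient on ibrutinib longer than a site that applies the rule to the same results. The cost is extra months on a drug for which section 7.8 lists serious risks, and uneven treatment duration between sites.

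**Working it through.** **Inputs, all from the Protocol**

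- Rule: double the time from start of ibrutinib to the first negative sample (7.2.3.1).
- Branch limits: first negative blood at 12 to 18 months (7.2.3.1).
- First example: 12 + 12 = 24. Second example: 15 + 15 = 30 (7.2.3.1).
- Lag from first negative blood to marrow: up to 6 months in 7.2.3.1; 6 months on the schedule in 7.2.3.

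**Step 1. Reproduce the stated totals.** The first example is 2 × 12 = 24, with the blood at Month 12 as the date doubled. This matches the rule. The second is 2 × 15 = 30, with the marrow at Month 15 as the date doubled. The 30 is obtained only by doubling the marrow date, or by assuming that the first negative blood was also at Month 15.

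**Step 2. Apply the rule to a marrow at Month 15.** Let L be the lag in months from first negative blood to marrow. The first negative blood is at 15 − L, so:

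- rule total = 2 × (15 − L)
- excess of the example = 30 − 2 × (15 − L) = 2L

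| Lag L | First negative blood | Inside 12-18 branch? | Rule total | Example total | Excess |
|---|---|---|---|---|---|
| 0 | Month 15 | yes | 30 | 30 | 0 |
| 1 | Month 14 | yes | 28 | 30 | 2 |
| 2 | Month 13 | yes | 26 | 30 | 4 |
| 3 | Month 12 | yes | 24 | 30 | 6 |
| 6 | Month 9 | no | not stated | 30 | not defined |

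Inside the branch the first negative blood must be at Month 12 or later, so L is at most 3 and the excess is 0 to 6 months. At L = 3 it is 6/24 = 25% of the course that the rule prescribes.

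**Step 3. A patient who fits both examples.** First negative blood at Month 12 and confirming marrow at Month 15 is a lag of 3 months, which the 6-month limit in 7.2.3.1 allows. The first example gives 24 months for this patient and the second gives 30.

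**Step 4. Compare with the schedule in 7.2.3.** Three bloods 3 months apart, with the marrow at the third, put a Month 15 marrow after bloods at Months 9, 12 and 15. First negativity is then at Month 9, below the branch's lower limit. On the protocol's own schedule, the second example therefore describes a patient to whom the branch does not apply.

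**The case against.** The strongest reply uses the protocol's own definition. Confirmation is dated from the first negative blood, so a patient described as confirmed at 15 months could be one whose first negative blood was at Month 15. Then 15 + 15 = 30 agrees with the rule. It may be added that the word for later assessment can be read as applying to the blood alone, and that the monotherapy rule speaks of a first negative sample without saying blood.

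This reading does not fit the line as written. The example dates a marrow, directly beneath an example that dates a blood sample, and section 7.2.3 places the marrow with the third blood, 6 months after the first. If first negative blood at Month 15 was intended, the arithmetic is right but the wording is still wrong, and the same correction applies.

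The second reply is that the rule itself is unambiguous and a site should not let one illustration override it. That stands. It makes this a drafting slip in one line and not a flaw in the stopping policy.

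A reader might also infer that the example lengthens treatment by 12 months, since twice a 6-month lag is 12. The documents do not support that. For a marrow at Month 15, a 6-month lag puts first negativity at Month 9, where no monotherapy duration is stated. Reaching 12 months inside the branch means applying the example's starting point to marrows at other times, which no text in the protocol does. The same objection rules out comparing totals across branches on a marrow date: that would turn one illustration into a general rule.

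**Conclusion.** The second monotherapy example in 7.2.3.1 is wrong as written. It doubles time to the confirming marrow where the rule doubles time to the first negative sample. Within the branch it exceeds the rule by 0 to 6 months, and by the full 6 (24 against 30) when first negative blood is at Month 12 and the marrow at Month 15. The size rests on two things: the marrow at Month 15 is taken literally, and the first negative blood lies inside the 12-18 month branch.

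The practical effect is minor. Section 12.2.2 expects a negligible proportion of MRD-negative patients on ibrutinib alone. The initial phase has 40 patients, of whom up to 20 relapsed/refractory patients may move to the extension study, where the combination rules apply. Ibrutinib also stops only if the patient is still MRD negative at the end of the extra period. The primary endpoint of the initial phase is assessed at or before 6 months and the extension decision rule concerns the combination regimen, so neither changes. Totals under the two readings part only from Month 24, so 1- and 2-year progression-free survival are essentially unaffected.

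**What to change.** Restate the second example in 7.2.3.1 with the date that the rule uses. Suggested content: a patient whose first MRD-negative blood is at Month 15, with the remission later confirmed by blood and marrow, takes 15 more months of ibrutinib, 30 months in all. This keeps the existing figures.

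An alternative is first negative blood at Month 18: 18 more months, 36 in all. Month 18 is a routine blood sampling visit in section 7.2.2 (Month 12 and six-monthly after that) and lies at the upper end of the branch.

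The change is one line of text. It needs no new visits, samples or patients and leaves the analysis as it is.
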